5.4 Patient Demographics and Frequency of Adverse Drug Reactions / Infections by Treatment

5.4.1 Patients demographics and Frequency of Adverse Drug Reactions / Infections by Treatment

(1) Patients to be tabulated and analyzed

Safety Analysis Set

(2) Details of tabulation and analysis

Each parameter will be categorized by the categories described below to tabulate the percent of patients with adverse drug reactions, etc.

The Fischer exact test will be used for parameters without rank data. The Mann-Whitney U test will be used for parameters with rank data. (The tests will be used for parameters with asterisk [*].)

Total and mild type 2 diabetes mellitus patients will be tabulated.

Parameter	Category
Sex*	Male, Female
Age*	< 65 years, ≥65 years
	< 75 years, ≥75 years
Severity of renal impairment*	Normal + Mild, Moderate + Severe
Concurrent liver disorder*	No, Yes
Concurrent renal disorder*	No, Yes
Concurrent heart disease*	No, Yes
Details of concurrent heart disease	Cardiac failure, myocardial infarction, or angina pectoris

Parameter	Category
(overlapped)	
Concurrent cardiac failure*	No, Yes
Severity classification of cardiac failure (NYHA classification)*	Classes NYHA I, NYHA II, NYHA III, and NYHA IV
Concurrent stroke-related disease*	No, Yes
Mean daily dose of Nesina	> 25 mg, 25 to >12.5 mg, 12.5 to > 6.25 mg, or ≤6.25 mg
Administration of concomitant medication (diabetic drug)	No, Yes
Concomitant medications (diabetic drugs) (overlapped)	α-glucosidase inhibitors, thiazolidines, sulfonylureas, biguanides, rapid-acting insulin secretagogues, or insulin preparations
Administration of concomitant medication (protease drug)*	No, Yes
Administration of concomitant medication (combined with renal excretory drug)*	No, Yes

(3) Number of tables and figures

Table 5.4.1-1

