## 1.0 Surveillance Background

The goal of diabetes mellitus treatment is to maintain patients' QOLs as those in healthy people and to secure their lifetimes through management for a favorable blood glucose level for a long time. In particular, early drug treatment is considered important for patients with mild type 2 diabetes mellitus, which maintains a favorable blood glucose level and inhibits the diabetes progress, along with prevention of microangiopathy.

As an oral drug started to be administered early to patients with mild type 2 diabetes mellitus, the desirable drug should have a low risk of hypoglycemia, be well tolerable, and not exhaust pancreatic function.

DPP-4 inhibitors selectively inhibit DPP-4, increase blood GLP-1 levels, and prompt the pancreas to secrete insulin in a glucose level-dependent manner. Taken together, DPP-4 inhibitors are expected to be highly effective for patients with mild type 2 diabetes mellitus. As a DPP-4 inhibitor, Nesina tablets (generic name: alogliptin benzoate) are confirmed to be highly effective and safe when administered alone and combined with various oral diabetic drugs in clinical studies conducted in Japan. The following are approved indications for Nesina:

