1.4 Level of Significance and Confidence Coefficient

Two-sided 5%, two-sided 95%.

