5.4 Patient Demographics and Frequency of Adverse Drug Reactions / Infections by Treatment

5.4.1 Patients demographics and Frequency of Adverse Drug Reactions / Infections by Treatment

(1) Patients to be tabulated and analyzed

Safety Analysis Set

(2) Details of tabulation and analysis

Each parameter will be categorized by the categories described below to tabulate the percent of patients with adverse drug reactions, etc.

The Fischer exact test will be used for parameters without rank data. The Mann-Whitney U test will be used for parameters with rank data. (The tests will be used for parameters with asterisk [*].)

Total and mild type 2 diabetes mellitus patients will be tabulated.

Parameter	Category
Sex*	Male, Female
Age*	< 65 years, ≥65 years
	< 75 years, ≥75 years
Severity of renal impairment*	Normal + Mild, Moderate + Severe
Concurrent liver disorder*	No, Yes
Concurrent renal disorder*	No, Yes
Concurrent heart disease*	No, Yes
Details of concurrent heart disease	Cardiac failure, myocardial infarction, or angina pectoris

Parameter	Category
(overlapped)	
Concurrent cardiac failure*	No, Yes
Severity classification of cardiac failure (NYHA classification)*	Classes NYHA I, NYHA II, NYHA III, and NYHA IV
Concurrent stroke-related disease*	No, Yes
Mean daily dose of Nesina	> 25 mg, 25 to >12.5 mg, 12.5 to > 6.25 mg, or ≤6.25 mg
Administration of concomitant medication (diabetic drug)	No, Yes
Concomitant medications (diabetic drugs) (overlapped)	α-glucosidase inhibitors, thiazolidines, sulfonylureas, biguanides, rapid-acting insulin secretagogues, or insulin preparations
Administration of concomitant medication (protease drug)*	No, Yes
Administration of concomitant medication (combined with renal excretory drug)*	No, Yes

(3) Number of tables and figures

Table 5.4.1-1

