5.5 Occurrence of Adverse Drug Reactions / Infections by Age

(1) Patients to be tabulated and analyzed

Safety Analysis Set

(2) Details of tabulation and analysis

Age will be classified into < 65 years, ≥65 years and < 75 years, and ≥75 years for tabulation of type of adverse drug reactions, etc.

The method for tabulation of adverse drug reactions, etc. is same as that described in Section 5.1.

Total and mild type 2 diabetes mellitus patients will be tabulated.

(3) Number of tables and figures

Tables 5.5-1 to 5.5-2

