1.2 Important Identified Risks, Potential Risks, and Missing Information

Term	Definition
Important identified risk	
Hypoglycemia	Adverse events of the following PT Codes (term) are defined as hypoglycemia. 10020994(Hypoglycaemia neonatal) 10040576(Shock hypoglycaemic) 10021000(Hypoglycaemic coma) 10020993(Hypoglycaemia) 10065981(Hypoglycaemic unconsciousness) 10021002(Hypoglycaemic encephalopathy) 10048803(Hypoglycaemic seizure) 10020997(Hypoglycaemia unawareness) 10077216(Hyperinsulinaemic hypoglycaemia) 10059035(Postprandial hypoglycaemia)
Acute pancreatitis	Adverse events of the SMQ Code 20000022 (acute pancreatitis (SMQ) narrow scope are defined as acute pancreatitis.
Hepatic impairment / jaundice	Adverse events of the SMQ Code 20000005 (hepatic disorders (SMQ) broad) are defined as hepatic impairment / jaundice.
Skin disorder including oculomucocutaneous syndrome (Stevens-Johnson syndrome) / erythema multiforme	Adverse events of the SMQ Code 20000020 (severe skin adverse reactions (SMQ) narrow) are defined as skin disorder including oculomucocutaneous syndrome (Stevens-Johnson syndrome) / erythema multiforme.
Rhabdomyolysis	Adverse events of the SMQ Code 20000002 (rhabdomyolysis/myopathy (SMQ) narrow) are defined as rhabdomyolysis.
Intestinal obstruction	Adverse events of the SMQ Code 20000105 (gastrointestinal obstruction (SMQ) narrow) or the HLGT Code 10018008 (gastrointestinal stenosis and obstruction) or HLT Code 10052736 (non-mechanical ileus) are defined as intestinal obstruction.
Interstitial pneumonia	Adverse events of the SMQ Code 20000042 (interstitial lung disease (SMQ) narrow) are defined as interstitial pneumonia.
Angioedema	Adverse events of the SMQ Code 20000024 (angioedema (SMQ) narrow) are defined as angioedema.
Important potential risk	
Infection	Adverse events of SOC Code 10021881(infections and infestations) are defined as infection.
Malignant tumor	Adverse events of the SOC Code 10029104 (neoplasms benign, malignant and unspecified (incl cysts and polyps)) are defined as malignant tumor.
Malignant tumor (narrow)	Adverse events of the SMQ Code 20000194 (malignant tumors (SMQ)

Term	Definition
sense)	narrow) are defined as malignant tumor (narrow sense).
Pemphigoid	Adverse events of the PT Code 10067776 (ocular pemphigoid) or 10034277 (pemphigoid) are defined as pemphigoid.

Term	Definition
Important missing information	

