5.1.3 Important Identified Risks, Important Potential Risks, and Important Missing Information

- (1) Patients to be tabulated and analyzed

Safety Analysis Set

- (2) Details of tabulation and analysis

The following will be tabulated for important identified risks, important potential risks, and important missing information (described in Section 1.2).

Total and mild type 2 diabetes mellitus patients will be tabulated.

Parameter	Details of tabulation and analysis
Number of patients with adverse events (or adverse drug reactions, etc.)	Number of patients who experienced adverse events (or adverse drug reactions, etc.) with important identified risks, important potential risks, and important missing information.

Parameter	Details of tabulation and analysis
Number of adverse events (or adverse drug reactions, etc.)	Number of adverse events (or adverse drug reactions, etc.) with important identified risks, important potential risks, and important missing information. Count as an event if the same adverse event (or adverse drug reaction, etc.) (LLT) occur multiple times in a patient. Count as different events for different LLTs even if they have the same PT.
Percent of patients with adverse events (or adverse drug reactions, etc.)	Described in Section 1.1.
Type of adverse events (or adverse drug reactions, etc.)	Will be broadly divided into the important identified risks, important potential risks, and important missing information and tabulated by PT in them. For the PTs, the number of adverse events (or adverse drug reactions, etc.) and percent of adverse events (or adverse drug reactions, etc.) will be described in the ascending order of PT codes. Count as an event if the same adverse event (or adverse drug reaction, etc.) (LLT) occur multiple times in a patient. Count as different events for different LLTs even though they have the same PT.

- (3) Number of tables and figures
Tables 5.1.3-1 and 5.1.3-2

5.2 Occurrence of Adverse Events and Adverse Drug Reactions / Infections in the Not Safety Analysis

Set

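### Safety factors are tested only on any adverse drug reaction, and no by-factor table combines the hypoglycaemia terms into a patient count, so a factor acting only on hypoglycaemia is diluted

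*SAP*

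**What the plan says.** SAP 5.4.1 sets the outcome for the safety-factor analysis: "Each parameter will be categorized by the categories described below to tabulate the percent of patients with adverse drug reactions, etc". On method it says "The Fischer exact test will be used for parameters without rank data", with a Mann-Whitney test for ranked factors, and "The tests will be used for parameters with asterisk". The starred rows are sex, age, severity of renal impairment, liver, renal, heart and stroke-related disease, cardiac failure and its NYHA class, protease inhibitors and renal excretory drugs. The rows for heart-disease detail, mean daily dose, any concomitant diabetic drug and diabetic-drug class have no star. SAP 1.4 sets a two-sided 5% level.

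SAP 1.2 lists hypoglycaemia first among the important identified risks: "Adverse events of the following PT Codes (term) are defined as hypoglycemia", followed by ten terms. SAP 5.1.3 gives patients per risk group, for the total and mild populations only.

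Sections 5.5 to 5.19 tabulate the type of ADR by factor. Each says: "The method for tabulation of adverse drug reactions, etc. is same as that described in Section 5.1". In SAP 5.1.2 the row for type of ADR counts patients at system organ class (SOC) level and reactions at PT level. A lowest level term (LLT) repeated in one patient counts once, and two LLTs under one PT count twice.

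The 5.4.1 wording quoted here is the same in the current SAP text, in Version 2.0 and in Version 1.0.

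**The concern.** Protocol 1.0 says of an early oral drug for mild disease that "the desirable drug should have a low risk of hypoglycemia, be well tolerable, and not exhaust pancreatic function". Protocol 9.5 puts hypoglycaemia first among the events for which detailed information is sought, and Protocol 10.4.2 asks which factors affect safety.

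The only tested outcome mixes hypoglycaemia with every other reaction. If a factor changes hypoglycaemia alone, the unrelated reactions add noise and pull the pooled ratio towards 1. If it raises one kind of reaction and lowers another, the two can cancel. A null result in Table 5.4.1-1 would then say little about who becomes hypoglycaemic, and no other planned table gives that as a patient count.

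**Working it through.** **The plan's own figures.** Protocol 3.2 gives 600 patients to identify an ADR of frequency 0.5% with 95% confidence. ln(0.05)/ln(0.995) = 597.6, so 598; the rule of three gives 3/0.005 = 600; and 1 − 0.995^600 = 0.951. The therapy counts sum to 1864 + 226 + 175 + 273 + 109 = 2647, and 20,000 × 273/2647 = 2063 for sulfonylureas, as stated. Both reproduce. They concern seeing a reaction at least once. The documents state no power for any factor comparison.

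**Where a hypoglycaemia patient count could come from.**

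| Place in SAP | By factor? | What it gives for hypoglycaemia |
|---|---|---|
| 5.1.3 | No | Patients, ten PTs combined |
| 5.4.1 | Yes | Nothing separate; inside any ADR |
| 5.5 to 5.19 | Yes | Up to ten PT rows of reactions; patients only for the whole SOC |

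**Inputs for the dilution.** From the documents: N = 20,000 (Protocol 3.1), Fisher's exact test (SAP 5.4.1), two-sided 5% (SAP 1.4). Assumed: factor in 10% (2,000 against 18,000); hypoglycaemia ADRs 0.3% without the factor, ratio 3; other ADRs 3% in both groups and independent of hypoglycaemia.

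**Pooled outcome.** P(any) = 1 − (1 − P(other))(1 − P(hypo)).
- Without the factor: 1 − 0.97 × 0.997 = 3.29%
- With the factor: 1 − 0.97 × 0.991 = 3.87%
- Ratio: 3.87/3.29 = 1.18, against a true hypoglycaemia ratio of 3

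**Power by simulated Fisher tests** (results move by a few points between runs):

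| Assumed case | Any ADR | Hypoglycaemia |
|---|---|---|
| As above | 28% | 94% |
| Other ADRs 1% | 54% | 94% |
| Other ADRs 5% | 18% | 93% |
| Factor in 5% | 18% | 74% |
| Factor in 20% | 42% | 99% |
| Ratio 2 | 10% | 52% |
| Base rate 0.1%, ratio 3 | 7% | 56% |

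At a 0.1% base rate and ratio 2, power on hypoglycaemia itself is about 24%; at 0.05% and ratio 3, about 34%. At the other end, with a 50:50 factor, base rate 0.5% and ratio 3, a normal approximation gives about 100% for hypoglycaemia and 81% to 99.9% for any ADR as other ADRs fall from 5% to 1%. There the loss can be negligible.

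**The case against.** Protocol 10.4.2 asks for ADRs in general by factor and names no risk, so the SAP does what the protocol requires. No hypothesis about predictors of hypoglycaemia is stated. This stands: nothing planned is invalid, and the point is an improvement.

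Several stronger readings are tempting, and the documents do not support them.

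- **Hypoglycaemia is invisible by factor.** It is not. Its PT rows appear by age (5.5), renal severity (5.9) and diabetic-drug class (5.17). With one count per LLT per patient, each row is an upper bound on patients with that PT. What is missing is the combined patient count, its percent and an interval.
- **No SAP 1.2 risk group has patient counts by factor.** Infection and malignant tumor are each defined as a whole SOC, so 5.5 to 5.19 already give patients with those ADRs by factor.
- **The sulfonylurea and insulin tests are diluted.** Those rows have no star, so there is no test to dilute; only the displayed percentage is affected. The classes also overlap and are not exclusive groups.
- **The survey is certainly large enough.** At a 0.1% base rate, power on hypoglycaemia is only about 24% to 56% for ratios of 2 to 3.

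Sections 5.5 to 5.19 cite Section 5.1 as a whole, which formally includes 5.1.3. But they tabulate only the type of ADR, and most plan a single table per factor where 5.1.3 plans two. The SOC and PT layout is the natural reading, and a clarification would help in any case.

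**Conclusion.** The point holds in limited form. The only tested safety outcome is any ADR, and no by-factor table turns the ten hypoglycaemia PTs into patients. For a factor acting on hypoglycaemia alone, pooling lowered power in every assumed case: 28% against 94% in the main case, 7% against 56% at a 0.1% base rate, and almost no loss when hypoglycaemia is common and other reactions are few. These sizes are illustrative. They rest on assumed rates, on the factor leaving other reactions unchanged, and on all 20,000 patients being analysed. A null result in Table 5.4.1-1 should not be read as showing that a factor has no bearing on hypoglycaemia.

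**What to change.** 1. **Correct the ADR definition first.** SAP 1.1 defines ADRs, and serious ADRs, as events the investigator judged not related to Nesina. Reword both so that they count events whose relation to Nesina is not ruled out, consistent with Protocol Table 3. Otherwise the new outcome inherits the error.
2. **Add a second outcome to Table 5.4.1-1:** number and percent of patients with hypoglycaemia (SAP 1.2 list) as an ADR in each category, with a 95% confidence interval. State that the denominator is the stratum, because the percent formula in SAP 1.1 divides by the whole Safety Analysis Set.
3. **Include each diabetic-drug class** as user against non-user, because the classes overlap.
4. **Label it exploratory** and keep the any-ADR analysis unchanged. Counts and intervals close the gap without further significance tests.

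No added rows are needed in 5.5 to 5.19 for risk groups defined as a whole SOC. The cost is SAP wording and extra table rows, with no new data. The downside is a larger number of exploratory comparisons to read with care.

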5.5 Occurrence of Adverse Drug Reactions / Infections by Age

(1) Patients to be tabulated and analyzed

Safety Analysis Set

(2) Details of tabulation and analysis

Age will be classified into < 65 years, ≥65 years and < 75 years, and ≥75 years for tabulation of type of adverse drug reactions, etc.

The method for tabulation of adverse drug reactions, etc. is same as that described in Section 5.1.

Total and mild type 2 diabetes mellitus patients will be tabulated.

(3) Number of tables and figures

Tables 5.5-1 to 5.5-2

5.6 Occurrence of Adverse Drug Reactions / Infections by Sex

(1) Patients to be tabulated and analyzed

Safety Analysis Set

(2) Details of tabulation and analysis

Sex will be classified into male or female for tabulation of type of adverse drug reactions, etc.

The method for tabulation of adverse drug reactions, etc. is same as that described in Section 5.1.

Total and mild type 2 diabetes mellitus patients will be tabulated.

(3) Number of tables and figures

Table 5.6-1

5.7 Occurrence of Adverse Drug Reactions / Infections by Liver Disorder

(1) Patients to be tabulated and analyzed

Safety Analysis Set

(2) Details of tabulation and analysis

Concurrent liver disorder will be classified into yes or no for tabulation of type of adverse drug reactions, etc.

The method for tabulation of adverse drug reactions, etc. is same as that described in Section 5.1.

Total and mild type 2 diabetes mellitus patients will be tabulated.

(3) Number of tables and figures

Table 5.7-1

5.8 Occurrence of Adverse Drug Reactions / Infections by Presence of Concurrent Renal Disorder

(1) Patients to be tabulated and analyzed

Safety Analysis Set

(2) Details of tabulation and analysis

Concurrent renal disorder will be classified into yes or no for tabulation of type of adverse drug reactions, etc.

The method for tabulation of adverse drug reactions, etc. is same as that described in Section 5.1.

Total and mild type 2 diabetes mellitus patients will be tabulated.

- (3) Number of tables and figures

Table 5.8-1

5.9 Occurrence of Adverse Drug Reactions / Infections by Severity of Renal Impairment

- (1) Patients to be tabulated and analyzed

Safety Analysis Set

- (2) Details of tabulation and analysis

Severity of renal impairment will be classified into normal + mild or moderate + severe for tabulation of type of adverse drug reactions, etc.

The method for tabulation of adverse drug reactions, etc. is same as that described in Section 5.1.

Total and mild type 2 diabetes mellitus patients will be tabulated.

- (3) Number of tables and figures

Table 5.9-1

5.10 Occurrence of Adverse Drug Reactions / Infections by Presence of Concurrent Heart Disease

- (1) Patients to be tabulated and analyzed

Safety Analysis Set

- (2) Details of tabulation and analysis

Concurrent heart disease will be classified into yes or no for tabulation of type of adverse drug reactions, etc.

The method for tabulation of adverse drug reactions, etc. is same as that described in Section 5.1.

Total and mild type 2 diabetes mellitus patients will be tabulated.

- (3) Number of tables and figures

Table 5.10-1

5.11 Occurrence of Adverse Drug Reactions / Infections by Presence of Concurrent Heart Failure

- (1) Patients to be tabulated and analyzed

Safety Analysis Set

- (2) Details of tabulation and analysis

Concurrent heart failure will be classified into yes or no for tabulation of type of adverse drug reactions, etc.

The method for tabulation of adverse drug reactions, etc. is same as that described in Section 5.1.

Total and mild type 2 diabetes mellitus patients will be tabulated.

- (3) Number of tables and figures

Table 5.11-1

5.12 Occurrence of Adverse Drug Reactions / Infections by Severity of Heart Failure

- (1) Patients to be tabulated and analyzed

Safety Analysis Set

- (2) Details of tabulation and analysis

Severity of heart failure will be classified into Class NYHA I, NYHA II, NYHA III, or NYHA IV for tabulation of type of adverse drug reactions, etc.

The method for tabulation of adverse drug reactions, etc. is same as that described in Section 5.1.

Total and mild type 2 diabetes mellitus patients will be tabulated.

- (3) Number of tables and figures

Table 5.12-1

5.13 Occurrence of Adverse Drug Reactions / Infections by Presence of Concurrent Stroke-related Disease

- (1) Patients to be tabulated and analyzed

Safety Analysis Set

- (2) Details of tabulation and analysis

Concurrent stroke-related disease will be classified into yes or no for tabulation of type of adverse drug reactions, etc.

The method for tabulation of adverse drug reactions, etc. is same as that described in Section 5.1.

Total and mild type 2 diabetes mellitus patients will be tabulated.

- (3) Number of tables and figures

Table 5.13-1

5.14 Occurrence of Adverse Drug Reactions / Infections by Mean Daily Dose of Nesina

- (1) Patients to be tabulated and analyzed

Safety Analysis Set

- (2) Details of tabulation and analysis

The mean daily dose of Nesina will be classified into > 25 mg, 25 to > 12.5 mg, 12.5 to > 6.25 mg, or ≤6.25 mg for tabulation of type of adverse drug reactions, etc.

The method for tabulation of adverse drug reactions, etc. is same as that described in Section 5.1.

Total and mild type 2 diabetes mellitus patients will be tabulated.

- (3) Number of tables and figures

Table 5.14-1

5.15 Occurrence of Adverse Drug Reactions / Infections by Mean Daily Dose of Nesina in Patients with Special Demographics (Patients with Moderate or Higher Renal Impairment)

(1) Patients to be tabulated and analyzed

Patients with moderate or higher renal impairment in the Safety Analysis Set

(2) Details of tabulation and analysis

The mean daily dose of Nesina will be classified into > 25 mg, 25 to > 12.5 mg, 12.5 to > 6.25 mg, or ≤6.25 mg for tabulation of type of adverse drug reactions, etc.

The method for tabulation of adverse drug reactions, etc. is same as that described in Section 5.1.

Total and mild type 2 diabetes mellitus patients will be tabulated.

(3) Number of tables and figures

Table 5.15-1

5.16 Occurrence of Adverse Drug Reactions / Infections by Administration of Concomitant Medication (Diabetic Drug)

(1) Patients to be tabulated and analyzed

Safety Analysis Set

(2) Details of tabulation and analysis

Administration of concomitant medication (diabetic drug) will be classified into yes or no for tabulation of type of adverse drug reactions, etc.

The method for tabulation of adverse drug reactions, etc. is same as that described in Section 5.1.

Total and mild type 2 diabetes mellitus patients will be tabulated.

(3) Number of tables and figures

Table 5.16-1

